Following confirmation of ischemic or hemorrhagic stroke, study investigators will determine patient eligibility for inclusion in the study. The investigators will administer questionnaires to collect patient health history and perform blood tests to measure physical health characteristics. Questionnaires will follow the Get with the Guidelines® survey intake forms of the American Heart Association, as developed in preliminary studies. Blood tests will be comprehensive: Testing for HIV will include CD4 count and viral load (HIV ELISA and Uni-GoldTM) performed at MNH; serum sodium, potassium, liver tests, creatinine, and hemoglobin A1c will be tested; women of childbearing potential will have a B-HCG test. Participants will be screened for dysphagia.

Participants will be screened by study physicians upon presentation for eligibility according to the following exclusion criteria: (1) NIH Stroke Scale Score >20 points, (2) unconscious at presentation, (3) transient ischemic symptoms <24h, (4) history of recent head trauma, (5) baseline motor deficits from other etiologies including prior stroke, and (6) patients who are moribund for other reasons and unlikely to survive to 90 days will also be excluded from participation. Additionally, (7) contraindication to MRI (e.g. piercings/tattoos, electronic/metallic implants, claustrophobia). All assessments of exclusion criteria/safety will be conducted by trained, IRB-approved study neurologists who are familiar with the procedures.

If a patient is found eligible, he or she will be approached, in person, by Tanzanian study coordinators and presented with the opportunity to enroll in the study.

IV. Subject Enrollment:

Consent will be obtained after confirmation both of acute ischemic or hemorrhagic stroke and patient eligibility criteria. A trained study staff member who is a licensed physician, without prior clinical connection to the patient, will be present in person to administer consent forms either in Swahili or English. Since there is limited outpatient stroke care prior to a new-onset stroke, we do not anticipate familiarity between the neurologist on duty at MNH and the newly admitted patients.

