All 90-day assessments will be administered by senior site investigators, who will also take the final 10-15mL blood draw, evaluate participant mRS, and inquire about adverse events. Participants will receive a second MRI brain at 90-days and will be administered the MoCA and IDEA screens. As at baseline, the 90-day Fugl-Meyer assessment will be filmed and stored on an encrypted external hard drive. In the case of aberrant scores or difficulty scoring, the video will be shown to expert study staff for validation of the correct Fugl-Meyer score.

It is possible that during the 90-day raft of questionnaires, participants will endorse survey questions that indicate suicidality. In such cases, participants will be formally referred to the study-site neurologist for psychiatric care and thorough psychological evaluation. Participants

will be referred to the managing neurologist because the number of psychiatrists in Dar Es Salaam is very low.

It may be necessary to drop certain participants from the study. In such cases, Tanzanian site investigators will evaluate the participant's continued participation in the study according to the following drop criteria: (1) participants who develop a serious, non-stroke related disease, like cancer, that will alter their life or seriously affect their medicine regimen; (2) participants who die; (3) participants who are lost to follow-up, defined as not being available during three attempts at contact 3 days apart over the course of 9 days; (4) participants who are unconscious or bed-ridden, defined as having an mRS score of 5 or greater; and (5) participants who become pregnant.

If a participant meets any drop criteria, Tanzanian site investigators will send a proposal, in writing, to U.S. site investigators to withdraw the participant from the study. U.S. site investigators will respond within 24 hours. When approved by U.S. site investigators, the participant will be formally withdrawn from the study. In cases where a participant develops a serious non-stroke related disease, he or she will be referred to appropriate physicians at MNH. In cases of death, loss to follow-up, or unconsciousness, Tanzanian site investigators will make a reasonable attempt to discover the circumstances surrounding participant withdrawal. Participant withdrawal will be noted in a Withdrawal Log alongside a brief explanation.

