Potential risks due to higher than usual standard of care: Participants in this study will be exposed to a better than normal standard of care. This includes access to physical and neuroimaging exams that may normally be outside patients' financial reach. There is a risk of identifying a previously unknown serious medical illness or subclinical finding on brain imaging. Such a finding could cause a participant to be worried, anxious, or scared; however, discovery of an unknown, potentially life-threatening condition will prompt immediate care. The care that patients then receive will be at least as good as usual care, if not significantly better due to institution of systematized evaluations, documentation, free neuroimaging and blood tests, documentation of clinical course, and access to a team of expert physicians throughout the course of the study.

Potential risks related to data safety and security: Participants will be exposed to risk of loss of confidentiality and breach of privacy. Such risks are related to the collection and maintenance of study data, the collection of video recordings of study procedures, and the collection of blood samples. These risks will be protected against via secure software purchases, secure data storage, training of study subjects in confidentiality best practices, and disclosure to participants of the intent to maintain data security at all times. All files of recordings of Fugl-Meyer assessments will be labeled only through participant ID.

Unanticipated problems involving or giving rise to risks to subjects, including adverse events, will be reported to the Partners Healthcare Research Council (PHRC) in accordance with PHRC unanticipated problems reporting guidelines.

VIII. Potential Benefits:

There are multiple benefits to the participants of this study, including accessibility to more expertise, efficiencies in the M NH healthcare system, access to physicians, and expert-provided care. In several cases, participants may be better treated and their underlying conditions better addressed. Some may go on to receive neurosurgical intervention or have a diagnosis that is treatable (e.g. diagnosis of liver disease).

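### Drop criteria 1 and 5 can end outcome collection for living participants in an observational 90-day cohort, while entry rules admit similar non-moribund disease and leave pregnancy unresolved

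*Combined protocol and SAP*

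**What the plan says.** **Entry (Sections III and IV).** Section III lists seven exclusions. Only the sixth deals with serious illness other than stroke: "patients who are moribund for other reasons and unlikely to survive to 90 days will also be excluded from participation". Pregnancy is not on the list. The screening bloods include a pregnancy test ("women of childbearing potential will have a B-HCG test"), but no consequence of a positive result is given. The seventh exclusion is "contraindication to MRI (e.g. piercings/tattoos, electronic/metallic implants, claustrophobia"; its examples do not include pregnancy. The enrolment conditions in Section IV cover age, confirmed stroke, consent, contact and reachability, and say nothing about comorbidity or pregnancy.

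**Follow-up (Section V).** The drop rules open with "It may be necessary to drop certain participants from the study". Criterion 1 covers "participants who develop a serious, non-stroke related disease, like cancer, that will alter their life or seriously affect their medicine regimen"; criterion 5 covers "participants who become pregnant". Once a criterion is met, the Tanzanian site must send a written withdrawal proposal. Then: "When approved by U.S. site investigators, the participant will be formally withdrawn from the study". For criterion 1 the protocol adds a referral to physicians at the hospital; for criterion 5 it adds nothing. Each withdrawal is recorded in a log with a short explanation. No outcome assessment after withdrawal is described.

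**Purpose (Sections V and VI).** The study is described as observational, concerned with cognition over the 90 days after stroke, with completed 90-day follow-up as its endpoint. Section VI assumes 30% mortality, leaving 140 of 200 alive at day 90. It gives no method for missing outcomes.

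**The concern.** A natural-history study should describe what happens to the people its entry criteria admit. New serious disease in the 90 days after a stroke is part of that history. No treatment is assigned, so a change in a participant's medication does not contaminate a treatment comparison.

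Under the current rules, a participant with non-moribund cancer at enrolment contributes a day-90 result, whereas one who develops cancer during follow-up must be proposed for withdrawal. If that is approved before day 90, the later participant's cognition, function, mood and quality of life are not recorded. Those results are plausibly worse than average, so the loss is probably not random. The results for aims 1 and 3 would then describe a group somewhat different from the cohort enrolled, and probably somewhat healthier.

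For pregnancy the numbers matter less than the gap in the rules. The condition is tested for at entry with no stated consequence, yet its later occurrence is a ground for withdrawal.

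**Working it through.** **1. The two sets of rules side by side.**

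| Condition | At entry (Sections III, IV) | Arising during follow-up (Section V) |
|---|---|---|
| Serious other disease, moribund | Excluded | Criterion 1, if it meets the wording |
| Serious other disease, not moribund | Not excluded | Criterion 1: proposal to withdraw |
| Pregnancy | Tested; consequence not stated | Criterion 5: proposal to withdraw |
| Serious disease already present, first found after enrolment | Not addressed | Not addressed: criterion 1 speaks of disease that develops |

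The second and third rows are the mismatch. The fourth is a gap that Section VII makes relevant: "There is a risk of identifying a previously unknown serious medical illness or subclinical finding on brain imaging".

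**2. The plan's own figure.** Inputs from Section VI: 200 enrolled, 30% mortality.

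200 × (1 − 0.30) = 140. This reproduces the stated number. It allows for deaths only; nothing is set aside for the other drop criteria.

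**3. Number of living participants affected.** The documents give no rate for criteria 1 and 5. The rate f below is an assumption.

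Number lost = f × 140. Half-width of a 95% interval for a proportion of 0.5 = 1.96 × √(0.25 / n).

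| Assumed f | Lost | Remaining n | Half-width (percentage points) |
|---|---|---|---|
| 0 | 0 | 140 | 8.3 |
| 2% | 2.8 | 137.2 | 8.4 |
| 5% | 7.0 | 133.0 | 8.5 |
| 10% | 14.0 | 126.0 | 8.7 |

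Even at 10%, the half-width grows by only 0.4 points, so precision is not the issue.

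**4. Bias.** If a fraction f of survivors is removed, the estimate among the rest differs from that in all survivors by f × (result in those kept − result in those removed). Suppose cognitive impairment were 30 percentage points more frequent in those removed, which is an assumption for illustration:

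- f = 2%: 0.02 × 30 = 0.6 points
- f = 10%: 0.10 × 30 = 3.0 points

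The estimated frequency of impairment would be too low by that amount. Both the rate and the 30-point difference are assumed. The calculation shows the order of size and does not predict it.

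**The case against.** Several points on the other side stand and limit what can be said.

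- **Onset, not discovery.** A reader might infer that the same condition is kept or dropped purely by when it is detected. The criteria refer to participants who develop a disease or become pregnant, so they turn on when the condition arises. On pre-existing disease found late, the text is silent.
- **The study's own tests.** A reader might infer that the extensive testing will itself trigger criterion 1. The head CT, HIV tests, HbA1c and baseline liver tests belong to screening, so what they reveal is generally known at entry. Only the two MRIs and the follow-up sodium and hepatic enzymes come after consent, and the second MRI is done at day 90.
- **Withdrawal is not automatic.** The opening wording is discretionary and U.S. approval is needed. Against this, the proposal is mandatory once a criterion is met, and no standard for approval is given.
- **Retention of prevalent disease is not guaranteed.** Section IX allows withdrawal at investigator discretion, so a participant with disease at entry could still be removed.
- **A possible rationale.** Disease at entry is a baseline characteristic, while new disease can alter the change being measured, such as Fugl-Meyer change from enrolment to completion. That is a fair reason to identify these participants and analyse them both ways. It does not require their outcomes to go uncollected.
- **Pregnancy at screening.** A reader might infer that a woman with a positive test is enrolled. The documents do not say so. The list of MRI contraindications is introduced as examples, so pregnancy could be meant to fall under it. The correct statement is that the consequence is unstated.

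The withdrawal log means the number removed can be counted, but it does not recover their outcomes.

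**Conclusion.** The concern holds in a limited form. The entry and drop rules treat non-moribund serious disease differently according to whether it is present at entry or arises later, and the pregnancy rules are incomplete at entry and explicit afterwards. Because nothing is collected after withdrawal, criterion 1 can selectively remove living participants' day-90 outcomes from a study whose purpose is to describe those outcomes.

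The effect is probably small: about 3 to 14 of the 140 expected survivors under an assumed 2% to 10%, with almost no effect on precision. The direction, towards a healthier group, is plausible for criterion 1 and rests on the assumption that newly ill participants do worse. No direction is claimed for pregnancy.

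The documents do not support a claim that the day-90 results are seriously biased, that every such participant will be lost, or that either criterion must be deleted. What they support is a worthwhile, inexpensive correction.

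**What to change.** 1. In Section V, distinguish stopping study procedures from ending outcome observation. For criteria 1 and 5, log the event and its date, and still collect the day-90 cognitive, functional, mood and quality-of-life measures where consent and safety allow.
2. In Section VI, report the day-90 results with these participants included and flagged, and add a sensitivity analysis that leaves them out.
3. Reconcile Sections III and V on pregnancy, including what follows a positive screening test, and on serious disease that was present at enrolment but first found afterwards. Which procedures continue, and which eligibility rule applies, is for the sponsor and ethics committee.

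**Cost.** A short protocol amendment and a few more day-90 assessments (at most the 3 to 14 assumed above). Some day-90 results will reflect intercurrent disease, which the flag and the sensitivity analysis make visible.

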A more thorough appreciation of stroke and its etiologies is likely both to lead to better clinical care and to inform new directions for care at MNH. Participants will receive free head CT imaging to potentially identify unrecognized and untreated causes of stroke. This could lead to improved health knowledge and more selected treatment approaches and care.

At MNH, training and knowledge of stroke, clinical research, and neuroimaging will occur throughout this study. Neurological research and focused expert neurological care post-stroke are nearly non-existent in Tanzania. Therefore, initial care provisions for brain disorders will provide foundational knowledge of neurological care to health care workers. This is likely to lead to better medical care for future patients with stroke who are not involved in the study.

II. Specific Aims:

(1) To calculate the cognitive outcomes, as measured by the SIDSA and MoCA for 90 days post-stroke in 200 participants. (2) To collect medical history survey data from 200 participants. (3) To calculate other variables of interest to the study population, including motor recovery (Fugl Meyer, modified Rankin scale), depression (PHQ-9, Asberg Depression Scale), lab variables (serum sodium, ALT), and quality of life (Stroke Impact Scale).

III. **Subject selection:**

Both male and female subjects greater than 18 years old and subjects from any racial and ethnic group may be enrolled in the study. Tanzania is an ethnically homogenous country; nearly all residents are ethnically Tanzanian. Therefore, in practice we expect little to no enrollment of other ethnicities and races beyond Tanzanian Africans. Recruitment of an approximately 1:1 male to female ratio is expected. Total recruitment is aimed at 200 participants with new-onset acute ischemic or hemorrhagic stroke presenting at Muhimbili National Hospital (MNH) within 21 days of symptomatic onset.

No children will be enrolled in the study. The mechanisms of stroke in pediatric age groups are presumed to be very different (e.g. non- atherosclerotic) and are outside the scope of the study question.

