Participants will have initial cognitive capacity measured through the MoCA scale and IDEA scale, administered in English or Kiswahili per patient preference.

Study participants will be contacted within three days of the 30-, 60-, and 90-day time-points to schedule an in-person visit, either at the hospital or at the participant's home. At each study visit, participants will be evaluated for medication and evaluated for adverse side-effects through verbal inquiry on the part of the investigator; investigators will draw 10-15mL of blood, in order to perform sodium and hepatic enzyme labs; investigators will assess participant disability through the modified Rankin Scale (mRS).

Analysis of serum sodium and hepatic enzyme levels will be conducted at MNH. Blood samples will also be shipped to the US for analysis of biomarkers of post-stroke cognitive decline.

If participants are unable to be reached in person during the 30- and 60-day follow-up visits, they will be called by Tanzanian site investigators. During these calls, investigators will evaluate the mRS of the participant and will inquire about adverse side-effects. The 90-day follow-up will occur either at MNH or at participants' home, whichever location was indicated as preferable during the screening and consent process.

Study Design: This study will be an observational trial to determine cognitive outcomes for 90 days following acute ischemic/hemorrhagic stroke in Tanzania. 200 patients presenting to Muhimbili National Hospital (MNH) with acute stroke will be enrolled. Subjects will be followed at 30, 60, and 90 days. The study endpoint will be considered as completion of the 90-day follow-up. Subjects will be remunerated the Tanzanian Schilling equivalent of 50 USD.

Objectives: (1) To calculate the cognitive outcomes, as measured by the SIDSA and MoCA for 90 days post-stroke in 200 participants. (2) To collect medical history survey data from 200 participants. (3) To calculate other variables of interest to the study population, including motor recovery (Fugl Meyer, modified Rankin scale), depression (PHQ-9, Asberg Depression Scale), lab variables (serum sodium, ALT), and quality of life (Stroke Impact Scale).

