Payment will be provided to participants. Payment will be the equivalent of 50 USD, approximately 116,000 Tanzanian Shillings. We expect this amount to fully cover the costs of transportation to and from the MNH.

VI. Biostatistical Analysis:

Data will include stroke motor-function recovery, cognition, serum sodium and hepatic enzyme laboratories, and quality-of-life/depression data, which will be captured, respectively, through changes in the Fugl-Meyer motor assessment between study enrollment and completion, through the IDEA and MoCA assessments, and through both the Asberg Depressive Symptom and PHQ-9 questionnaires.

The number of participants has been chosen based on an estimated natural history from our pilot observation work. A post-stroke mortality of approximately 30% at 90 days is assumed. Of n=200 enrolled participants, 140 are assumed to be alive at 90 days.

VII. Risks and Discomforts:

Risks associated with blood draws: During venous blood draws the skin is pierced by a needle. Any insult to the skin can result in discomfort, pain, and bruising. There is a slight risk of infections associated with blood draws. Risks will be minimized through the use of established blood-draw safety protocols, including exclusive use of sterile needles and use of alcohol swabs to disinfect the skin area that the needle will pierce.

Risks associated with MRI: During MRI, patients can experience discomfort due to the loud noises and closely enclosed space of the machine. Risks will be minimized by explaining MRI procedures to patients. MRI is also known to be safe and used in routine stroke clinical care in the US.

Potential psychological stress/discomfort: There exists a risk of incurring psychological discomfort due to diagnostic questions about mood. Discomfort includes embarrassment, anxiety, panic, or depression. In the event of severe psychological distress, subjects will be promptly referred to appropriate mental health experts.

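### Death is a ground for withdrawal and is given no place on the modified Rankin scale, so the day-90 functional result would by default describe survivors only

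*Combined protocol and SAP*

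**What the plan says.** Section V (Study Procedures) lists five drop criteria. The second is "2) participants who die". The others are serious non-stroke disease, loss to follow-up, severe disability and pregnancy. For any of them the Tanzanian site sends a written proposal, and then: "When approved by U.S. site investigators, the participant will be formally withdrawn from the study". The case goes into a Withdrawal Log. The fourth criterion reads "4) participants who are unconscious or bed-ridden, defined as having an mRS score of 5 or greater", so the protocol itself uses the mRS as having a level above 5.

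The Study Design paragraph in section V states "200 patients presenting to Muhimbili National Hospital (MNH) with acute stroke will be enrolled" and "The study endpoint will be considered as completion of the 90-day follow-up". Aim 3 in section II includes "motor recovery (Fugl Meyer, modified Rankin scale" among its outcomes. Section V has senior site investigators evaluate the day-90 mRS at the 90-day visit.

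Section VI (Biostatistical Analysis) states "A post-stroke mortality of approximately 30% at 90 days is assumed" and "Of n=200 enrolled participants, 140 are assumed to be alive at 90 days". Its description of the data does not mention the mRS, and it defines no analysis population and no handling of withdrawn participants. Section IX classes death as a serious adverse event, to be reported within 24 hours of site awareness. Adverse events are logged with an onset date.

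**The concern.** The study exists to describe what happens to people after a stroke in this setting, and the protocol expects nearly a third of them to die within the observation period. Yet death is handled administratively, through the same withdrawal procedure as pregnancy or failed contact. A participant who dies on day 40 may have a day-30 mRS but has none at day 60 or day 90, and no rule supplies one.

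If the mRS is then tabulated on those with a day-90 value, the worst outcome leaves both numerator and denominator. The result is more favourable than the outlook for a newly enrolled patient. It can also move the wrong way: the more severely affected participants die, the better the remaining distribution looks. With no written rule, the choice between all enrolled and survivors as denominator could be made after the data are seen.

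**Working it through.** **Inputs**
- Enrolled: N = 200 (section V, Study Design).
- Assumed 90-day mortality: m = 0.30 (section VI).
- Stated number alive at day 90: 140 (section VI).
- Distribution of mRS among survivors: not given, so the favourable share p below is an assumption.

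**Step 1: the plan's own figure.** N × (1 − m) = 200 × 0.70 = 140. This reproduces the stated number. Deaths: 200 − 140 = 60, or 30% of the cohort.

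**Step 2: who has a day-90 mRS.** The value comes from an assessment at the visit, death leads to withdrawal, and no rule assigns a score. At most 140 participants have a value; 60 do not.

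**Step 3: effect on a favourable proportion.** A participant who died does not count as favourable, so share of all enrolled = p × 140/200 = 0.70p. The overstatement is p − 0.70p = 0.30p.

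| Assumed p among survivors | Share of all enrolled | Difference (points) |
|---|---|---|
| 30% | 21% | 9 |
| 40% | 28% | 12 |
| 50% | 35% | 15 |
| 60% | 42% | 18 |
| 70% | 49% | 21 |

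**Step 4: sensitivity to the mortality assumption.** If the true rate were exactly 30%, the 95% sampling range at N = 200 is 0.30 ± 1.96 × √(0.30 × 0.70/200), about 24% to 36%, or 47 to 73 deaths. If the true rate were 20% to 35% (assumed), 40 to 70 participants would have no day-90 mRS.

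**Step 5: interaction with criterion (4).** The factor 0.70 needs all 140 survivors to be assessed, but criterion (4) also drops living participants at mRS 5. If 5%, 10% or 15% of survivors (assumed) were dropped for this reason, 133, 126 or 119 would remain. The factor applied to the assessed group would then be 0.665, 0.63 or 0.595, and 33.5%, 37% or 40.5% of the cohort would have no value.

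**The case against.** The strongest reply is that withdrawal from a study is not exclusion from its analysis. Section V ends participation; no sentence removes anyone from a denominator, and no mRS analysis is written. The sentence that calls completed follow-up the study endpoint comes directly after the visit schedule and may only mark the end of a participant's follow-up. This stands. A reader might infer that the sponsor plans to report survivors only, but the document does not support that. It supports the narrower statement that the written procedure leaves deaths without a score and nothing puts them back.

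A reader might also infer that deaths are lost among other withdrawals. They are not. The circumstances of a death are to be sought, the reason is logged, and each death is a serious adverse event with an onset date. The information exists but is not designated as an outcome.

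Third, the mRS is one of several aim 3 variables. Cognition is the lead aim, and no hypothesis test or sample-size result depends on the mRS. That limits the weight of the point; it does not remove it.

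Last, the illustrative sizes rest on assumed survivor proportions and a planning mortality rate. Section III also excludes patients with an NIH Stroke Scale score above 20, those unconscious at presentation, and those not expected to live through the 90 days, so actual mortality may differ. A survivor proportion that is clearly labelled is a different quantity rather than an error. The difficulty here is that nothing requires the label.

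**Conclusion.** The point holds as a gap with a predictable direction, and it should be fixed before analysis. Followed as written, the protocol leaves about 60 of 200 participants (30%, its own assumption) without a day-90 mRS, and the result would by default describe survivors. Leaving deaths out cannot lower a favourable proportion and raises any that is above zero.

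The factor 0.70 rests on 30% mortality and on all 140 survivors being assessed. The 9 to 21 points rest, in addition, on assumed survivor proportions of 30% to 70% and are an illustration, not an estimate of bias in this study. Criterion (4) would change the gap further.

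Two stronger conclusions are not supported: that the plan expressly excludes deaths from analysis, and that the cognitive aim is invalidated. For the cognitive scales the need is clear labelling, since aim 1 speaks of 200 participants while section VI expects 140 alive.

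**What to change.** 1. In the drop-criteria text of section V, state that death ends study procedures but does not remove the participant from the outcome analysis. The criterion need not be deleted if this distinction is made.
2. In section VI, name death, with its date, as a study outcome.
3. In section VI, state that a participant who has died takes the death category of the mRS at day 90 and at any scheduled visit after the death, and name that category, since the protocol does not print the scale.
4. Report mortality and the mRS with all enrolled participants as the denominator, and say how missing values among living participants, including those dropped under criterion (4), are shown.
5. Label MoCA, IDEA and Fugl-Meyer results as results among survivors, and print the number who died beside them.

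The cost is wording. Deaths and their dates are already captured through serious adverse event reporting and the adverse events log, so no new data collection is needed. The one downside for the sponsor is that the reported functional outcome will look less favourable.

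### Drop criterion 4 makes mRS 5 or greater, a value of an aim 3 outcome, a ground for withdrawal, and the plan describes no day-90 assessment or counting rule for survivors withdrawn this way

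*Combined protocol and SAP*

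**What the plan says.** Section V (Study Procedures) describes the design: "This study will be an observational trial to determine cognitive outcomes for 90 days following acute ischemic/hemorrhagic stroke in Tanzania". Aim 3 (Section II, repeated under Objectives in Section V) lists the mRS with the Fugl-Meyer as measures of motor recovery. The mRS is assessed at days 30, 60 and 90, with a telephone assessment at days 30 and 60 if the participant cannot be seen in person. The follow-up cognitive testing comes at day 90: "Participants will receive a second MRI brain at 90-days and will be administered the MoCA and IDEA screens". The repeat Fugl-Meyer is also done then.

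The drop rules in Section V open with "It may be necessary to drop certain participants from the study". Criterion 2 is death. Criterion 4 reads "4) participants who are unconscious or bed-ridden, defined as having an mRS score of 5 or greater". When any criterion is met, the site is to put a withdrawal proposal in writing to the U.S. investigators. Then: "When approved by U.S. site investigators, the participant will be formally withdrawn from the study". Every withdrawal is entered in a Withdrawal Log with a short reason. In addition: "In cases of death, loss to follow-up, or unconsciousness, Tanzanian site investigators will make a reasonable attempt to discover the circumstances surrounding participant withdrawal".

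Section VI measures motor recovery "through changes in the Fugl-Meyer motor assessment between study enrollment and completion" and cognition by IDEA and MoCA. It does not mention the mRS, an analysis population, missing data or withdrawn participants. Its only account of losses is "Of n=200 enrolled participants, 140 are assumed to be alive at 90 days".

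**The concern.** A study meant to describe outcome after stroke should not stop measuring people because their outcome is poor. Death is a separate criterion, so what criterion 4 adds is the withdrawal of living participants, and it selects them on a value of a study outcome. If approval comes at day 30 or 60, the plan describes no day-90 mRS, MoCA, IDEA or Fugl-Meyer for that person.

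At stake is whether the day-90 results describe all survivors or only those who stayed below mRS 5 at the earlier visits. Section VI has no rule that would make a report state which of these it shows.

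**Working it through.** **1. The plan's own figure.** Section VI assumes 30% mortality at 90 days. 200 × (1 − 0.30) = 140 survivors, and 200 − 140 = 60 deaths. The 140 reproduces exactly, so it allows for death only and not for survivors withdrawn alive.

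**2. What remains after an approved withdrawal at day 30 or 60** (Sections V, VI and IX):
- Present: baseline data, the mRS that triggered the proposal, and the Withdrawal Log entry.
- Inquiry into circumstances: covers death, loss to follow-up and unconsciousness. A conscious bed-ridden participant is not named.
- Not described: any day-90 outcome assessment.
- Not stated: whether the person stays in a denominator, or how.

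**3. Number withdrawn (assumed rates).** Let f be the share of the 140 survivors who reach mRS 5 at day 30 or 60, and a the share of proposals approved. Neither is in the documents. W = 140 × f × a.
- f = 5%, a = 0.5: W = 3.5, leaving 136.5.
- f = 5%, a = 1: W = 7, leaving 133.
- f = 15%, a = 1: W = 21, leaving 119.

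**4. Effect on day-90 mRS (illustration).** The plan sets no good-outcome cut-off. Assume 60 of 140 survivors (42.9%) have a good outcome, and a share g of those withdrawn would have had one. Share among those remaining = (60 − gW)/(140 − W).
- f = 5%, a = 0.5, g = 10%: 59.65/136.5 = 43.7%, a factor of 1.02.
- f = 15%, a = 1, g = 0: 60/119 = 50.4%, a factor of 1.18.
- g = 42.9% (break-even): 42.9%, a factor of 1.00.
- f = 15%, a = 1, g = 60%: (60 − 12.6)/119 = 39.8%, a factor of 0.93.

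On the mean scale, with q = W/140, the mean among those remaining minus the mean in all survivors is q × (mean remaining − mean withdrawn). Assume those withdrawn would still score 5 at day 90 and those remaining average 2.0 to 3.0. At q = 5% mean mRS is too low by 0.10 to 0.15 points. At q = 15% it is too low by 0.30 to 0.45.

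**5. Cognition (bounds).** Assume 40% of retained survivors are impaired and all proposals are approved. The share in all survivors lies between (1 − f) × 0.40 and (1 − f) × 0.40 + f.
- f = 5%: 38% to 43%.
- f = 15%: 34% to 49%.

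Both intervals contain 40%, so arithmetic alone does not fix the direction.

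**6. Fugl-Meyer.** Section VI uses change from enrolment. Nothing in the documents says whether participants at mRS 5 would change more or less than the others, so no direction follows.

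**The case against.** **The loss is visible.** The Withdrawal Log covers every withdrawal, including conscious bed-ridden participants. Under Section IX, persistent or significant disability is a serious adverse event reported within 24 hours. The DSMB follows premature withdrawals and reviews retention and data completeness. This stands: withdrawn participants can be counted by reason. But none of these routes is tasked with obtaining day-90 outcomes, and the log is not said to record whether someone could have been tested.

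**Withdrawal is not automatic.** The opening of the drop rules is permissive, and approval is required. This stands in part. The later sentence words the written proposal as an obligation once a criterion is met, so the clear discretion lies in the approval, for which no criteria are given.

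**Silence is not a ban.** No text forbids later contact, orders earlier data to be discarded, or removes withdrawn participants from a denominator. This stands. A reader might infer that data collection is prohibited or that these participants vanish from the record. The documents support only that no later assessment is described and no counting rule is given.

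**Entry criteria limit the group.** NIHSS above 20, unconsciousness at presentation and moribund patients are excluded (Section III). That limits severity at presentation, not later worsening, and sets no mRS limit.

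**Some could not be tested anyway.** For participants too impaired for MoCA or IDEA, no score is lost. What is missing is a record that they were untestable.

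**The sizes are assumed.** This stands: the rates, the approval share and the outcome shares come from no passage.

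**Conclusion.** The gap holds on the text: criterion 4 is a stated ground for withdrawing living participants on an outcome value, with no day-90 assessment described afterwards and no rule in Section VI for counting them. Confidence in this is high. It should be fixed.

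The direction of bias is held with moderate confidence, and for day-90 mRS only. It requires that those withdrawn would on average have finished worse than those retained, which is plausible for people at mRS 5 but not derived from the documents. If criterion 4 is first met at the day-90 visit, the outcomes may already be recorded and the problem does not arise.

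Three stronger readings are tempting and unsupported. One is that all results would look too favourable: for MoCA and IDEA this is an expectation, and for Fugl-Meyer change it is not shown. Another is that the bias has a known size: the factors from 0.93 to 1.18 only illustrate assumed rates. The third is that criterion 4 is to blame for leaving deaths out of a denominator. That is a separate reporting matter (200/140 = 1.43).

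**What to change.** **Section V.** State that meeting criterion 4 does not by itself end outcome collection. For every living participant whose consent has not been withdrawn, seek at least mRS and vital status at day 90 by home visit, call or proxy contact. Where it applies, record MoCA, IDEA and Fugl-Meyer as not testable because of severity. Reconcile the permissive opening of the drop rules with the obligatory written proposal. Whether any study procedure stops at mRS 5 is left to the sponsor.

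**Section VI.** Account for all 200 enrolled at day 90. Report mRS with deaths, withdrawn (by reason) and unknown shown. Give cognitive and motor results among survivors beside the numbers dead, untestable and withdrawn. Scoring deaths as mRS 6 is an optional reporting choice and not needed to close this gap.

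**Cost.** Amendment wording, a short counting rule and some extra contacts. On the assumptions above, these are 3.5 to 21 survivors, plus vital-status contacts for participants withdrawn at mRS 5 who die before day 90. If 10-30% of the 60 assumed deaths were first at mRS 5, that is 6 to 18 people, of whom half or all are withdrawn. The total is 0.5 × (7 + 6) = 6.5 at the low end and 21 + 18 = 39 at the high end. Day-90 home visits, telephone mRS at days 30 and 60 and next-of-kin numbers are already in Sections IV and V; calls or proxies at day 90 would extend them. Recovery figures may become less favourable.
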